8.3.2 Time Period and Frequency for Collecting AE and SAE Information

Immediate Post-immunization Observation Period

Participants enrolled in the nirsevimab group will be kept under observation for 30 minutes after immunization to ensure their safety. The post-immunization observation should be documented in the source document.

Non-serious Adverse Events

Non-serious adverse events will be collected from dosing/randomization (D01) until 30 days after immunization, ie, D31.

The intensity grading scale for non-serious adverse events is presented in Appendix 10.2.5.1.

Medically Attended Adverse Events (MAAEs)

MAAEs will be collected from dosing/randomization (D01) to D366 phone call.

Adverse Events of Special Interest (AESIs)

AESIs will be collected from dosing/randomization (D01) to D366 phone call

See Section 8.3.7 for the list of AESIs.

SAEs

Information on SAEs will be collected and assessed throughout the study, from dosing/randomization (D01) until 12 months after immunization (D366) for all participants.

Information on related SAEs will be collected and assessed from D366 until D731 post-dosing/randomization for UK reconsented participants. Refer to Section 8.3.1 for the exemption of reporting LRTI hospitalizations as SAEs.

It is to be noted that, since this study is seeking real-world data, part of the participants' safety data will be collected retrospectively by the Investigator or designee. This means that, following the initial capture of information in the eDiary/memory aid by the parents or LARs, the Investigator or designee will be seeking additional or missing participant data from the medical facility where the medical visit or the hospitalization occurred to complete the corresponding eCRF.

All SAEs will be recorded and reported to the Sponsor or designee immediately and under no circumstance should this exceed 24 hours, as indicated in Appendix 10.2. The investigator will submit any updated SAE data to the Sponsor within 24 hours of it being available.

Investigators are not obligated to actively seek information on AEs or SAEs after conclusion of the study participation. However, if the investigator learns of any SAE, including a death, at any time after a participant has been discharged from the study, and he/she considers the event to be reasonably related to the study intervention or study participation, the investigator must promptly notify the Sponsor.

8.3.3 Method of Detecting AEs and SAEs

Individual eDiaries, specifically designed for this study by the Sponsor, will be made accessible to parents or LARs during Visit 01 at the study sites. The eDiaries will be used by parents or LARs to report health-related events occurring in participants, including unplanned medical visits and hospitalization. Individual memory aid will be provided to parents or LARs of UK reconsented participants to report any hospitalizations and emergency-room visits occurring from D366 to D731 post-dosing/randomization.

The Investigator or a designee may interview the parents or LARs to collect and clarify information recorded in the eDiary/memory aid. All clinical study information gathered by the study site and/or designee will be reported electronically by the Investigator or designee using a web-based eCRF. Any information that was not documented in the eDiary will first be captured in the source document and then reported electronically.

The 12-month follow-up will be done by interviewing by the investigator or delegated site staff all participants' parents or LARs over the telephone to capture SAEs, MAAEs, and AESIs, if applicable. The 18- and 24-month follow-up will be done by interviewing UK reconsented participants' parents or LARs over the telephone to capture related SAEs.

8.3.4 Follow-up of AEs and SAEs

After the initial AE/SAE report, the Investigator and/or delegated site staff is required to proactively follow each participant during subsequent contacts, unless parents or LARs refuse further contact. All AEs that are considered by the Investigator as serious or related to the study intervention administered, or AEs of special interest (as defined in Section 8.3.7), will be followed during the conduct of the study until resolution, stabilization, or the participant is lost to follow-up

(as defined in Section 7.3). For related SAEs ongoing at last study contact, such follow-up may need to continue after the end of the study.

Further information on follow-up procedures is provided in Appendix 10.2.

8.3.5 Regulatory Reporting Requirements for SAEs

- Prompt notification by the investigator to the Sponsor of an SAE is essential so that legal obligations and ethical responsibilities towards the safety of participants and the safety of a study intervention under clinical investigation are met.
- The Sponsor has a legal responsibility to notify both the local regulatory authority and other regulatory agencies about the safety of a study intervention under clinical investigation. The Sponsor will comply with country-specific regulatory requirements relating to safety reporting to the regulatory authority, Institutional Review Boards (IRB)/Independent Ethics Committees (IEC), and investigators.
- An investigator who receives an investigator safety report describing a SAE or other specific safety information (eg, summary or listing of SAEs) from the Sponsor will review and then file it and will notify the IRB/IEC, if appropriate according to local requirements.
- Investigator safety reports must be prepared for suspected unexpected serious adverse reactions (SUSAR) according to local regulatory requirements and Sponsor policy and forwarded to investigators as necessary.

8.3.6 Pregnancy

Not applicable as the study does not include women of childbearing potential.

8.3.7 Adverse Events of Special Interest

An AESI (serious or non-serious) is one of scientific and medical concern specific to the Sponsor's study intervention or program, for which ongoing monitoring and rapid communication by the investigator to the Sponsor can be appropriate. Such an event might warrant further investigation in order to characterize and understand it. Depending on the nature of the event, rapid communication by the study Sponsor to other parties (eg, regulators) might also be warranted.

The following AEs will be assessed as AESIs throughout the study:

- hypersensitivity, including anaphylaxis (56)
- immune complex disease (57)
- thrombocytopenia (58)

The designated Sponsor study representative will work with the investigator to ensure that all relevant information is provided and entered in the eCRF. If the event is considered serious, it must be reported to the Sponsor by the Investigator as an SAE, ie, no later than 24 hours of when she or he becomes aware of the event as an SAE (Appendix 10.2).

8.3.8 Medically Attended Adverse Events

MAAEs will be collected using the same process as other AEs.

See Appendix 10.2.1 for definition of MAAEs.

8.3.9 Health Measurement/Observation

Participants' parents or LARs will be able to report the occurrence of safety events in the eDiary during the first year of the study. In addition, and regardless of whether a safety event was captured during the month, there will be a monthly electronic contact with parents or LARs of the participant, via the eDiary application, to confirm that no health-related events went unreported during the month. The automated monthly electronic contacts will occur up to 6 months post-dosing/randomization. If parents or LARs of the participant confirm that a safety event occurred during the past month, a phone investigations by the site staff and/or designee will be triggered, and the data will be recorded in the eCRF.

At 12 months, a safety follow-up phone call will be made to the parents or LARs of the participant by the site personnel or designee.

Parents or LARs of UK reconsented participants will be able to report any hospitalizations and emergency room visits that occurred from D366 to D731 post-dosing/randomization in the memory aid.

8.4 Pharmacokinetics

Pharmacokinetics parameters are not evaluated in this study.

8.5 Genetics

Genetics are not evaluated in this study.

8.6 Biomarkers

No biomarkers are evaluated in this study.

8.7 Medical Resource Utilization

For participants who report LRTI hospitalizations during the study, the investigator or designee will collect data about health care resource utilization associated with medical encounters.

For each case of LRTI hospitalization, the data collected in the eCRF should:

- Include the RSV test result, the lowest rate of oxygen saturation recorded, the duration of
 hospital stay, the list of medical interventions leading to end of the hospitalization (eg,
 oxygen supplementation, intravenous fluid administration, admission to intensive care
 unit), and outcome, and
- Exclude procedures, tests, and encounters mandated by the protocol.

The sponsor may use the collected data to conduct economic analyses.

Medical Resource Utilization will be evaluated in this study as an exploratory objective to investigate the effectiveness of nirsevimab compared with no preventive intervention in reducing utilization of key medical resources. Data on medical resource utilization will be collected either directly (if the attending physician is the Investigator) or retrospectively from the host hospital and/or the attending physician (if the attending physician is not the Investigator) to identify and measure the impact on these key medical resources arising from RSV LRTI hospitalization in infants.

The evaluation of resource use will be based on RSV LRTI hospitalizations and duration of stay, utilization of oxygen supplementation, administration of intravenous fluid, and ICU admissions and duration of stay.

8.8 Immunogenicity Assessments

See Section 8.1.3.

9 Statistical Considerations

9.1 Statistical Hypotheses

The primary and key secondary efficacy objectives will be assessed in the Primary Analysis (see Section 9.4 for details of the Primary Analysis) by a hierarchical order. Details on statistical methods are provided in Section 9.4.

For the primary objective, a superiority approach will be used to assess the efficacy of nirsevimab in preventing RSV LRTI hospitalization through the RSV season compared to no intervention in all 3 countries combined. Only if the superiority for the primary endpoint is demonstrated, a superiority approach will be used to assess the efficacy of nirsevimab in preventing very severe RSV LRTI through the RSV season compared to no intervention in all 3 countries combined, and no multiplicity adjustment is needed for this.

If the superiority for very severe RSV LRTI through the RSV season is demonstrated, a superiority approach will be used to assess the efficacy of nirsevimab in preventing RSV LRTI hospitalization through RSV season compared to no intervention in each country separately. For this, Bonferroni adjustment of 2-sided α (ie, 0.05/3) is used to correct multiple testing in 3 countries in the sample size calculation and Bonferroni-Holm procedure will be used in the statistical analysis. For other secondary objectives and observational objectives, no hypotheses will be tested and the analyses will be descriptive.

9.2 Sample Size Determination

A total of 28 860 participants are expected to be enrolled of whom approximately 14 430 will receive nirsevimab and 14 430 will receive no intervention. This sample size is driven by the

demonstration of efficacy in preventing RSV LRTI hospitalization in each of 3 countries independently.

Based on the reported incidence rates of RSV LRTI hospitalization in France, Germany, and the UK (2) (51) (52), assuming a 1.1% incidence rate on average in the control group (ie, receiving no intervention), 9620 participants need to be enrolled in each of the 3 countries (which is equivalent to 74 events of RSV LRTI in each country) to ensure the 90% power to detect 60% efficacy in each country with a 2-sided α of 1.66% taking the multiplicity adjustment using Bonferroni approach into consideration.

The sample size of 28 860 participants has at least 99% power to detect 60% efficacy in preventing RSV LRTI hospitalizations in all 3 countries combined assuming an incidence rate of 0.86% in the control group (the lowest reported in the 3 countries) with a 2-sided α of 5%, and approximately 95% power to detect 60% efficacy in preventing very severe RSV LRTI defined in the protocol assuming an incidence rate of 0.4% in the control group (59) with a 2-sided α of 5%. To ensure at least 90% power for very severe RSV LRTI, at least 61 events are needed.

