A follow-up phone call will be made to the parents or LARs of the participant by the site personnel or designee at D366 (end of the study for France, Germany, and non-reconsented UK participants) to collect any safety event that may have occurred in the 6-month period since the last electronic contact.

Two additional follow-up phone calls – at D546 and D731 post-dosing/randomization (end of the study) – will be made to the parents or LARs of the UK reconsented participants by the site personnel to collect any LRTI hospitalizations or related SAEs that might have occurred from D366 to D731 post-dosing/randomization. A memory aid will be provided to the parents or LARs of the UK reconsented participants to record any of these events that may occur during the second year of the study.

During the 12- and 24-month follow-up calls, the site investigator or staff designee will ask to parents/LARs of UK reconsented participants if the participants had experienced any medically attended cough, chest or breathing problems throughout the study period. After the 12-month follow-up phone call (when possible) and the 24-month follow-up phone call, the site investigator or staff designee (including third parties authorized by the site investigators) will access the UK reconsented participants' medical record (general practitioner's or hospital's record) to determine if the medical event meets with the definition of wheeze provided by the Sponsor (see Section 8.1.2.4). If so, the event and related complementary information (including any medications prescribed during wheeze) will be retrospectively collected.

Number of Participants:

A total of 28 860 participants is expected to be randomized. This study is event driven.

For each country, at least 74 events of RSV LRTI hospitalization through the RSV season are needed to ensure the 90% power to conclude the efficacy of nirsevimab in preventing RSV LRTI hospitalization in that country, compared to no intervention, taking the multiplicity adjustment into consideration.

Intervention Groups and Duration:

Eligible participants will be randomized in a 1:1 ratio to receive a single IM injection of 50 mg (if weight < 5 kg) or 100 mg (if weight ≥ 5 kg) of nirsevimab or no RSV preventive intervention on D01. Randomization will be stratified by country and by age group at the time of randomization (ie, age ≤ 3.0 months, age > 3.0 to ≤ 6.0 months, and age > 6.0 months).

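### The 90% power claimed for each country holds at the 1.1% average incidence; at the plan's own lowest country rate, 0.86%, it is about 79% at the Bonferroni planning alpha and about 87% to 89% under the planned Holm procedure

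*Protocol*

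**What the plan says.** Protocol 9.2 and SAP 2.3 say that the sample size is driven by showing efficacy in each of the three countries independently. The per-country calculation is made "assuming a 1.1% incidence rate on average in the control group". From that rate the plan concludes that "9620 participants need to be enrolled in each of the 3 countries". It equates this number with 74 events per country, and the purpose it gives is "to ensure the 90% power to detect 60% efficacy in each country". The test level behind the figure is a 2-sided 1.66%, from a Bonferroni split over the three country tests.

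The next paragraph turns to the combined analysis and computes its power "assuming an incidence rate of 0.86% in the control group (the lowest reported in the 3 countries"). No per-country power is given at that lower rate, and section 9.2 does not list the rate assumed for each country.

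Protocol 9.1 distinguishes two multiplicity methods: Bonferroni (0.05/3) for the sample size, and Bonferroni-Holm for the analysis. SAP 6.6.4.2 sets out the Holm steps. The country tests come third in the hierarchy, after the combined primary endpoint and very severe RSV LRTI.

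**The concern.** The three country tests are run separately, each on its own country's events. The power of each is governed by that country's incidence. An average over three countries cannot support a statement about every one of them unless the rates are equal, and the plan's own text shows that they are not: at least one reported rate is 0.86%, below the 1.1% average.

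At stake is how a country result is read. These tests are key secondary, alpha-controlled comparisons, and the plan says they set the size of the trial. If one country does not reach significance, a reader who trusts the 90% figure will give that result more weight as evidence against efficacy than the design warrants.

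**Working it through.** **Inputs.** Protocol 9.2: 9,620 per country; 60% efficacy (rate ratio 0.4); 2-sided alpha 1.66%; control rates 1.1% and 0.86%. Protocol 1.1: "Eligible participants will be randomized in a 1:1 ratio", so 4,810 per arm. Protocol 9.4.2: exact binomial test of the nirsevimab events conditional on the total. No dropout allowance is stated and none is assumed.

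**Expected events.** Events = 4,810 × rate × (1 + 0.4).

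- At 1.1%: 4,810 × 0.011 × 1.4 = 74.1
- At 0.86%: 4,810 × 0.0086 × 1.4 = 57.9

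**Exact conditional test.** With equal person-time the nirsevimab share of events is 0.5 under the null and 0.4/1.4 = 0.286 under the alternative. At 2-sided 1.66% the test rejects with at most 26 nirsevimab events out of 74, or at most 19 out of 58. The Poisson column averages the power over a Poisson total with the expected mean.

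| Control rate | Expected events | Power at fixed total | Power, Poisson total |
|---|---|---|---|
| 1.1% | 74.1 | 91.4% (74 events) | 89.5% |
| 0.86% | 57.9 | 80.4% (58 events) | 79.0% |

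The first row reproduces the plan's 90%. The second is the same calculation with only the rate changed.

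**Cross-check, pooled two-proportion z.** Power = Φ{[√n(p1 − p2) − z√(2p̄(1 − p̄))] / √(p1(1 − p1) + p2(1 − p2))}, with n = 4,810 and z = 2.395.

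- At 1.1% against 0.44%: Φ[(0.4577 − 0.2961)/0.1235] = 90.5%
- At 0.86% against 0.344%: Φ[(0.3579 − 0.2621)/0.1093] = 81.0%

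Other variants at 0.86% give 77.2% (continuity-corrected) and 77.5% (Wald, log rate ratio). The Schoenfeld formula gives 86.2%, but it also gives 93.9% for the plan's own case, where the stated figure is 90%.

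**Under Holm.** The thresholds are 0.05/3, 0.025 and 0.05 for the ordered p-values, so a country's power depends on the other two. The results below come from simulation (400,000 trials per scenario, exact conditional p-values, 4,810 per arm in every country). Section 9.2 does not state the other countries' rates, so they are assumptions. The 1.6% is the German figure in Protocol 2.2, and 1.22% is the value that makes the three rates average 1.1%: (0.86 + 2 × 1.22)/3 = 1.10.

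| Assumed rates in the other two countries | Holm power in the 0.86% country |
|---|---|
| 0.86% and 0.86% | 87% |
| 0.86% and 1.6% | 88% |
| 1.1% and 1.1% | 88% |
| 1.22% and 1.22% | 89% |

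The ceiling can be found without simulation: if the 0.86% country were always tested at the full 0.05, exact power at 57.9 expected events would be 89.5%. For comparison, with all three countries at 1.1%, Holm power is about 95% in each.

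**Size needed at 0.86%.** On the Bonferroni basis, 90% power needs about 12,150 infants in that country (pooled z). Expecting 74 events needs 2 × 74/(1.4 × 0.0086) ≈ 12,290.

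**The case against.** The strongest reply is that nothing has been miscalculated. The 90% is stated as conditional on an average rate, it reproduces on that condition, and 0.86% is disclosed in the next paragraph. That stands. The fault lies in extending a result at the average to each country, not in the sum.

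Second, 79% is not the power of the analysis that will be run. A reader might infer an 11-point shortfall in the planned test. The documents do not support that, because Protocol 9.1 and SAP 6.6.4.2 specify Holm, under which the shortfall against 90% is about 1 to 3 points. The 79% is right only on the Bonferroni basis that the plan itself used for sizing, and it must be labelled so.

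Third, Protocol 1.1 calls the study event driven and says that "at least 74 events of RSV LRTI hospitalization through the RSV season are needed to ensure the 90% power". A reader might take this as a second instance of the fault. It is not: as an event requirement it holds at any incidence. Nor does it rescue the 9,620, since no rule holds a country open until it has 74 events. The Primary Analysis is triggered by 61 events in all countries combined, and no later than 30 April 2023 (Protocol 9.4.1, SAP 6.7.8).

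Fourth, a reader might go further and combine 0.86% with unequal enrolment. Protocol 4.2 says UK participants are half the study population. If the other two countries shared the rest equally, 7,215 infants in a 0.86% country would give 43 events and about 63% power. The documents do not support that figure. The 50% belongs to the rationale for the UK extension, no French and German split is given, and section 9.2 does not say which country has the 0.86% rate. If it were the UK, the same reading gives 14,430 infants and about 94% power.

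Last, the tests are third in the hierarchy, and the SAP already speaks of the Primary Analysis as done. A restatement changes no decision. It does change how a country result should be read.

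**Conclusion.** The point holds as a limit on a stated claim. Ninety percent power in each country is correct at 1.1%. At the plan's own lowest country rate it is about 79% at the Bonferroni planning alpha (77% to 81% across the methods that come close to the plan's 90%), and about 87% to 89% under Holm. Even Holm's most lenient step does not reach 90%.

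These figures assume 9,620 infants in the country, equal allocation, 60% efficacy, equal person-time and no dropout. The Holm range also depends on the assumed rates elsewhere and ignores the need to pass the two earlier tests first.

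The combined primary test is not affected: at 0.86% with 14,430 per arm, 14,430 × 0.0086 × 1.4 = 173.7 events are expected and power exceeds 99.9%.

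**What to change.** In Protocol 9.2 and SAP 2.3, replace the single sentence on power in each country with a table giving, for each country, the assumed control incidence, expected events at 9,620, and power on the Bonferroni and Holm bases. State the claim as 90% at 1.1% (Bonferroni basis) and, at 0.86%, about 79% (Bonferroni) or about 87% to 89% (Holm), with the assumed rates in the other countries shown. Leave the 74-event requirement in Protocol 1.1 as it is.

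The cost is wording in two documents and a less favourable stated figure. No test, endpoint, alpha level or study procedure changes. If the documents are no longer open to amendment, the same table can go in the clinical study report beside the country results.

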Severe RSV bronchiolitis requires treatment in the intensive care unit more often than bronchiolitis caused by other pathogens in particular due to necessity to utilize high flow nasal cannula respiratory support (41) (42) (43). Severe RSV acute respiratory infections are also a significant contributor to pediatric mortality (37) (44) (45), especially in infants younger than 3 months of age (46). Infants with clinically significant preexisting neuromuscular impairment are at an increased risk for a complicated course of RSV infection and an increased RSV-related mortality which underscores the indication for passive immunization in these vulnerable patients (47) (48). In a comparative study, RSV infection in early infancy showed a more severe clinical course than COVID-19 (49).

France

Data on RSV-associated hospital admissions in children < 5 years of age during the 2010-2018 period were extracted from the French national hospital discharge database (Programme de Médicalisation des Systèmes d'Information – PMSI). On average, 45 225 RSV-associated hospitalizations per RSV season were reported in France, with 69% of hospitalizations among children < 1 year of age. This amounts to approximately 28% of hospitalizations occurring among children < 1 year of age during an RSV season (35).

Germany

Interpretation of secondary data and modelling results are supported by results from active surveillance and testing of LRTI in prospective hospital studies in Germany. The PRI.DE study, a population-based study of viral LRTI in children < 3 years of age, calculated incidence rates of 11 RSV hospitalizations per 1000 children (50). Similarly, a study of RSV-positive hospitalizations in children < 1 year of age in Kiel over a 7-year period described an incidence rate of 16 per 1000 in children (51).

UK

In the UK, the burden of RSV infections in children < 5 years of age was estimated and RSV was found to be responsible for 12 primary care consultations (95% confidence interval [CI]: 11.9; 12.1) and 0.9 admissions to the hospital (95% CI: 0.89; 0.90) annually per 100 children annually (52). The same study outlined that general practice (GP) consultations for RSV infections during the first year of life fluctuated between 13.9 per 100 children to up to 27.4 per 100 children for children born in March and November, respectively (52).

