4.1 Overall Design

The design of the study is summarized in Table 4.1.

Table 4.1: Overall design

Type of design	Open-label, multi-center, parallel 2-arm study: nirsevimab compared to no preventive intervention for RSV
Phase	IIIb
Control method	Comparison to no preventive intervention
Study population	Healthy infants born ≥ 29 weeks gestational age (WGA) entering their first RSV season and not eligible for palivizumab (born either in-season or out-of-season)
Level and method of blinding	Open-label
Study intervention assignment method	 Randomization will be stratified by the following: Country Age group at time of randomization (ie, age ≤ 3.0 months, age > 3.0 to ≤ 6.0 months, age > 6.0 months)
Number of participants	28 860 participants
Intervention groups	Eligible participants will be randomized in a 1:1 ratio to receive a single IM injection of 50 mg (if weight < 5 kg) or 100 mg (if weight ≥ 5 kg) of nirsevimab or no RSV preventive intervention on D01
Total duration of study participation	12 months post-dosing/randomization for France, Germany, and UK non-reconsented participants and 24 months post-dosing/randomization for UK reconsented participants
Countries	France, Germany, and the United Kingdom

Use of an Independent Data Monitoring	
Committee, Dose Escalation Committee, or	No
similar review group	

Study Calendar

- Planned date of first participant in: 01 September 2022
- Planned date of last participant in: 28 February 2023
- Planned date of last visit last participant: 28 February 2025

Note: As much as operationally feasible, the date of inclusion of the first participant will be aligned with the beginning of the RSV season. It is thus possible that the first participants are enrolled earlier than 01 September 2022.

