2.3. Sample Size and Power

A total of 28,860 participants are expected to be enrolled of whom approximately 14,430 will receive nirsevimab and 14,430 will receive no intervention. This sample size is driven by the demonstration of efficacy in preventing RSV LRTI hospitalization through RSV season in each of 3 countries independently.

Based on the reported incidence rates of RSV LRTI hospitalization in France, Germany, and the United Kingdom ^{1,2,3}, assuming a 1.1% incidence rate on average in the no intervention group, 9,620 participants need to be enrolled in each of the 3 countries (which is equivalent to 74 events of RSV LRTI in each country) to ensure the 90% power to detect 60% efficacy (see definition of efficacy of nirsevimab in preventing RSV LRTI hospitalization compared to no intervention in Section 2.4) in each country with a 2-sided α of 1.66% taking the multiplicity adjustment using Bonferroni approach into consideration.

The sample size of 28,860 participants has at least 99% power to detect 60% efficacy in preventing RSV LRTI hospitalizations in all 3 countries combined assuming an incidence rate of 0.86% in the no intervention group (the lowest reported in the 3 countries ^{1,2,3}) with a 2-sided α of 5%, and approximately 95% power to detect 60% efficacy in preventing very severe RSV LRTI defined in the protocol assuming an incidence rate of 0.4% in the no intervention

group with a 2-sided α of 5%. To ensure at least 90% power for very severe RSV LRTI, at least 61 events are needed.

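### The conversion of 9620 infants per country into 74 events and 90% power makes no allowance for enrolment during the season; at the plan's 1.1% it needs nearly all infants enrolled by season start

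*Protocol*

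**What the plan says.** Protocol 9.2 sizes the trial on the country tests, "assuming a 1.1% incidence rate on average in the control group" and aiming "to ensure the 90% power to detect 60% efficacy in each country". The planning level is a Bonferroni share of 5% over three countries, stated as 1.66% two-sided. It concludes that "9620 participants need to be enrolled in each of the 3 countries (which is equivalent to 74 events of RSV LRTI in each country"). SAP 2.3 repeats this: "9,620 participants need to be enrolled in each of the 3 countries (which is equivalent to 74 events of RSV LRTI in each country"). Neither section mentions an enrolment curve, the overlap of enrolment with the season, or drop-out, and Protocol 7.2 says that withdrawn participants are not replaced.

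Other sections fix the exposure:

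- Protocol 4.1 plans first inclusion on 1 September 2022, possibly earlier, and gives "Planned date of last participant in: 28 February 2023".
- Protocol 4.2 describes a typical season of about 5 months starting in October or November, and plans to enrol infants born in season as well as before it.
- Protocol 9.4.2 starts follow-up at randomization (control) or dosing (nirsevimab) and stops event-free follow-up at season end or at the last date confirmed event-free, if earlier. SAP 6.6.1 uses the 28 February 2023 cut-off as the season end.
- The Synopsis calls the study event driven and asks for at least 74 events per country. Protocol 9.4.1 and SAP 6.7.8 trigger the Primary Analysis at 61 events in the three countries combined, and no later than 30 April 2023.

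**The concern.** An infant enrolled in January has already passed part of the season, and one enrolled on 28 February adds almost no season risk under the SAP's end date. Some late entry is built in, because infants born in season can only be included after birth (Protocol 10.1.3). A calculation that credits every enrolled infant with the full rate therefore overstates the events, unless the 1.1% was already lowered for this or almost everyone is enrolled before the season.

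The event-driven label does not close the gap. Three countries at 74 events need 3 × 74 = 222 events, while the trigger is 61 combined, and no rule waits for 74 in any country.

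At stake is the property that sets the sample size, which is separate proof of efficacy in each country. The very severe test is affected too, and it must succeed before the country tests are opened. A non-significant country result would be misread if readers believed that the test had 90% power.

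**Working it through.** **Inputs from the documents.** 4810 infants per arm per country (9620 at 1:1); control rate 1.1%; efficacy 60%, so the rate ratio is 0.4; two-sided alpha 1.66%. For very severe RSV LRTI: 14 430 per arm, 0.4%, alpha 5%. For the combined primary endpoint: 14 430 per arm, 0.86%, alpha 5%.

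**Step 1: reproduce the plan.** Events per country = 4810 × (0.011 + 0.4 × 0.011) = 4810 × 0.0154 = 74.07. For power I use the plan's exact conditional test with equal person-time: a nirsevimab share of events of 0.5 under the null and 0.4/1.4 = 0.286 under the alternative. Power is 91.4% at exactly 74 events, and 89.5% averaged over a Poisson count with mean 74.07. A two-proportion formula gives 90.5%. So the stated figures reproduce if each infant carries the full 1.1%.

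The same method gives 14 430 × 0.0056 = 80.8 very severe events and 96.9% power (the plan says about 95%), and 14 430 × 0.01204 = 173.7 combined events at 0.86% with power above 99.9%.

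**Step 2: share of season risk after entry.** Assumptions not in the documents: uniform enrolment over the 181 days from 1 September to 28 February, constant infant risk, no drop-out. With flat risk over the season, the mean share f is:

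- October-February (151 days): 30/181 + (151/181) × 0.5 = 0.58
- November-February (120 days): 61/181 + (120/181) × 0.5 = 0.67
- November-March (151 days), counted to its end: 61/181 + (120/181) × (91/151) = 0.74
- November-March, counting stopped on 28 February: (61/181) × (120/151) + (120/181) × (60/151) = 0.53

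A triangular mid-season peak leaves the first two unchanged and gives 0.75 and 0.67 for the last two. The range is f = 0.53-0.75.

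**Step 3: events and power per country.** Events = 74.07 × f; power is exact, averaged over a Poisson count.

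| Enrolment, uniform from 1 September to | f | Events per country | Country power |
|---|---|---|---|
| 28 February (as planned) | 0.53-0.75 | 39-56 | 58-77% |
| 31 December | 0.69-0.95 | 51-70 | 73-87% |
| 31 October | 0.80-1.00 | 59-74 | 80-90% |

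**Step 4: the other tests, enrolment to 28 February.** Very severe: 80.8 × f = 43-61 events, power 78-91%; Protocol 9.2 itself asks for at least 61 events for 90%. Combined primary at 0.86%: 173.7 × f = 92-130 events, power about 98% or more.

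**Step 5: sensitivity to the rate.** At 1.6%, the German figure in Protocol 2.2, f = 0.6-0.7 gives 4810 × 0.016 × 1.4 × f = 65-75 events and 84-90% power. At 0.86%, which Protocol 9.2 calls the lowest reported rate, the same shares give 35-41 events and 50-59%.

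**The case against.** The strongest reply is that 1.1% is a planning value for the trial's own control arm. If it already reflects partial exposure, multiplying by f discounts twice. The documents do not settle this. Against the reply, Protocol 9.2 derives 1.1% from reported rates and, for the combined test, uses the lowest reported rate (0.86%) unchanged as the control-group rate.

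A reader might go further and infer that all the source rates are full-year figures whose mean is about 1.1%, which would prove that no discount was made. The documents do not support that. In Protocol 2.2 only the UK rate is called annual, and it covers children under 5; the German source "described an incidence rate of 16 per 1000 in children" under 1 year with no stated time base; no French rate is given.

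A reader might also infer that 28 860 infants cannot yield the stated events, or that the sum is wrong. Neither follows. The multiplication is right, 74 events do give about 90% power, and the enrolment curve is unknown. Protocol 4.1 aligns first inclusion with the season and allows a start before 1 September, and Protocol 4.2 speaks of possibly immunizing the intervention cohort at season start. That cannot cover infants born later in the season, but early enrolment of the rest would recover much of the loss, as the 31 October row shows.

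Offsets are real but unquantified. Protocol 2.2 reports first-year RSV consultations of 13.9 per 100 for March births and 27.4 for November births, so newborns enrolled in season may carry above-average risk; these are consultations, not admissions. The UK under-5 rate may also imply a higher infant rate. With five equal age cohorts and the French 69% infant share, both borrowed assumptions, it gives 0.9 × 5 × 0.69 = 3.1%. Even f = 0.53 would then yield 4810 × 0.031 × 1.4 × 0.53 = 111 events.

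Finally, the 28 February stop is the SAP's; Protocol 8.1.2.1 leaves season ends to country surveillance. The ranges above cover both.

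**Conclusion.** The concern holds as a conditional one. Protocol 9.2 and SAP 2.3 present 74 events and 90% country power as consequences of enrolling 9620 infants. If 1.1% is a full-season rate, they follow only when nearly all infants enrol by the start of the season, and the planned calendar does not ensure that. The size of the shortfall depends on the enrolment curve: modest if enrolment is almost complete by the end of October, substantial if it is spread evenly to the end of February. The very severe gate weakens alongside the country tests; the primary conclusion is hardly affected.

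The ranges rest on uniform enrolment, constant infant risk, no drop-out and the three season windows. Drop-out would lower them; a higher infant rate or higher newborn risk would raise them. They use the plan's Bonferroni alpha for comparability; the Holm procedure used in the analysis can be somewhat more powerful. They show how sensitive the design is and do not predict the event count.

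**What to change.** In Protocol 9.2 and SAP 2.3:

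1. Compute expected events as N × seasonal rate × expected share of season risk after enrolment, with a stated enrolment curve and drop-out rate.
2. State whether 1.1% is a full-season rate or one already reduced for partial exposure, and say how it was derived from the cited sources.
3. Restate expected events and power for the country and very severe tests as a range.
4. Replace the equivalence between 9620 infants and 74 events by a conditional statement: country power of 90% holds only if 74 events accrue in that country.

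This costs a short calculation and some text, with no extra participants. The downside is that the stated power becomes less favourable.
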